## Supplement S007

## Clinical Protocol

2. 4 SCI patients, 3 internalized [44]. Pain in individual patients was distributed: in both lower extremities below T10, in all extremities below C5, in both lower extremities below T9, in the right lower limb (n=1). The first three cases were implanted bilaterally in the ventrocaudalis thalamic nucleus; the fourth received one lead in ventrocaudalis and one in the PAG/PVG. The first, third and fourth patients were internalized and experienced benefits lasting from 2 months to 5 years.
3. 3 SCI patients, 1 internalized [45]. All sites were ST. “One case of lower limb pain after excision of a neurofibroma of the lumbar region and two cases of gunshot wounds causing partial paraplegia.” They “...experienced two early failures and one late failure because of tolerance development during the course of 2 years”.
4. 8 SCI cases, 3 internalized [46]. There were 2 long-term successes, characterized as “almost complete pain relief” and “the patient's ability to resume a normal pain-free life”. All sites appear to have been in ST (VPL).
5. SCI patients, 3 or 4 internalized [47]. The authors summarize their results as follows. “Fourteen electrodes, 7 sensory thalamic and 7 PAG/PVG, were implanted in 11 patients with pain secondary to spinal cord injury. Two of each class of electrodes were internalized (36%). No patient obtained long term pain relief with DBS”.
6. 6 SCI patients, 5 internalized [48]. One patient had excellent relief and two had partial relief. Injuries are not described. Sites were ST (VPL) with or without PVG or PAG stimulation.

This choice of sites reflected the view that ST should be targeted for neuropathic pain and PAG/PVG for nociceptive pain, since SCI pain is typically a mixture of nociceptive and neuropathic pain [49]. However, the neuropathic pain of SCI is mechanistically distinct from other central neuropathic pains (e.g. post-stroke or thalamic pain syndrome) [50].

Insertion of electrodes in the PAG/PVG is reported to cause short-term analgesia [44]. Yet insertion could quite likely produce the opposite effect in some participants, temporarily blocking the stimulation-produced analgesia, which would have been excluded by the selection criteria typically used, leading to underestimates of potential success rate.

In summary, the total number of reported cases involving DBS surgery for SCI pain was 44. Only 21 were internalized, that is, involved applying DBS beyond the neurosurgical operation. The majority of SCI pain cases were given stimulation in either the ST or the ST combined with the PAG/PVG. There are 3-4 cases of PAG/PVG stimulation without concomitant ST stimulation. Some of these were not typical spinal cord trauma. Thus existing data are too few to assess whether or not PAG/PVG stimulation is effective against SCI pain. Changes in other SCI symptoms were not described. A beneficial effect on autonomic dysreflexia is possible, since PAG/PVG stimulation inhibits the types of nociceptive pain that elicit it.

## 9 STUDY DEVICE

### 9.1 Device Description

The Activa PC Deep Brain System as shown in Figure 1 below consists of the neurostimulator, leads, extensions, and clinician and patient programmers. The Activa PC primary cell neurostimulator (model 37601) is a multi-programmable device that can deliver electrical stimulation through one or two leads implanted in the brain. Stimulation is provided by controlled delivery of current from a battery in an implantable neurostimulator (INS) to metal leads (electrodes) surgically implanted in the brain. The INS is typically placed in the pectoral location or near the collarbone. Current is conducted to the electrodes via electrical conduits, including extensions (Models 37085 and 37086) and leads (model 3387), which are tunneled subdermally through the neck, travel through the skull, and terminate in a neural structure appropriate to the neurological disease being treated. The Activa PC system is capable of providing stimulation to 2 leads, each with 4 electrode contacts. Stimulation parameters are adjusted to optimize therapy for the patient. They can be independently controlled and include the following: active electrode(s), electrode polarity, pulse width, amplitude, and frequency. The stimulation settings are stored in programs. A program is a specific combination of pulse width, rate, and amplitude settings acting on a specific electrode combination on a lead, or on a lead and the INS, in unipolar mode. Up to four programs can be combined into a group. Pulse width, amplitude, and electrode polarity are independently programmed for each program within a group. Rate, rate limits and cycling for each program within a group must have the same values. Stimulation is delivered to a maximum of two implanted leads (one lead per hemisphere), with a maximum of 4 electrodes per lead. Rate is limited to 250 Hz, pulse width is limited to 450  $\mu\text{sec}$ , amplitude is limited to 10.5 V (or 25.5 mA) and the charge density warning threshold is 30  $\mu\text{C}/\text{cm}^2/\text{phase}$ .

Stimulation programs are controlled by the clinician via the N'Vision Clinician Programmer. A patient programmer (model 37642) will enable the patient to deactivate the device and can output an event log.

[figure not shown]

Figure 5: Activa PC System

The Activa PC+S DBS Implantable System will have therapy equivalent to Activa PC. This equivalence includes stimulation capabilities (pulse width, rate amplitude, modes) and the use of the same model 8840 Clinician Programmer and software, model 37642 patient programmer, and leads as the Activa PC system. In addition, sensing capability is included in the Activa PC+S implantable neurostimulator (INS), which is the same from factor as Activa PC. Sensing is controlled and its data managed with a User-intuitive research interface, a Clinician Sensing Programmer. This tablet programmer interfaces to the INS via telemetry and to a personal computer via USB. The Clinician Sensing Programmer will not adjust or control therapy. Likewise, the 8840 Clinician Programmer and the two Patient Programmer models will not adjust or control Sensing. In addition, the Medtronic Activa PC+S 8180 Sensing Software will be used. Medtronic Activa PC+S 8180 Sensing Software is part of a neurostimulation system for deep brain stimulation used to exclusively program the Medtronic Activa PC+S Model 37604 Implantable Neurostimulator for sensing of brain electric field potential. The Activa PC+S Sensing Software system components consist of: the Activa PC+S 8180 Sensing Software, the 8181 Sensing Tablet, and the SPTM (Sensing Programmer Telemetry Module). The Medtronic Activa PC+S 8180 Sensing Software, along with the Sensing Tablet and the SPTM, uses telemetry, a radio-frequency (RF) communication, to configure, record, and retrieve sensing information obtained from the Medtronic Activa PC+S 37604 Implantable Neurostimulator.

[figure not shown]

Figure 6. Activa PC+S Sensing Software System

## 10 RISK ANALYSIS

The rationale for unilateral or bilateral DBS implants is based on the potential benefits that may be produced. For participants with chronic SCI, the benefits anticipated from DBS include reduction or alleviation of neuropathic pain. A beneficial effect on autonomic dysreflexia is also possible, since PAG/PVG stimulation inhibits the types of nociceptive pain that elicit it.

The risks of the device implant surgery (to the participants) in this study are identical and no more than those associated with current DBS surgery for Parkinson's treatment. The risks include, but are not limited to, bleeding, transfusion, infection, sensory impairment, paralysis, speech arrest, stroke, seizure, intracerebral hemorrhage, coma, and/or death. The participants will be made aware of the risks in writing and in person. These participants will all be consented prior to entering the study.

To minimize surgical risks, exposure to general anesthetic, and additional stereotactic frame placement in one cranial procedure (as opposed to two separate) will be used to implant bilateral devices. This approach falls under the standard of care for DBS neurosurgery.

There is potential throughout the study of adverse events occurring related to the implant itself. These include but are not limited to, erosion of the device through the skin, migration or movement of the hardware in the brain, delayed infection of the device, battery failure, and/or mechanical failure of the device. These complications may necessitate further surgery to correct. However, it is important to note that the safety profile of this device and the surgical procedure is well established, and investigator(s) are well trained and have previously conducted several hundred identical implant procedures.

### 10.1 Risk minimization

The study protocol contains several measures to minimize risk, many adopted based on the experience in standard DBS surgery (Parkinson's trial or other experiences that are relevant to the risk minimization measures that will be used). These include the design that the therapy is completely reversible (it can be fully explanted without damaging neuronal or muscular tissue). The user also has the ability to instantaneously turn off the device with the Patient Controller. Additionally, participants will have 24 hour access for contacting study personnel.

If subjects have an implanted programmable pump, such as an intrathecal baclofen (ITB) pump, risk will be minimized as follows. The neurostimulator (generator) will be placed at least 8 inches from the pump and/or on the opposite side of the body. Whenever the pump or neurostimulator is reprogrammed, each device will be checked before the patient leaves a programming session to ensure that the other device was not inadvertently affected. Patients will be told to contact their physician immediately if they experience symptoms (such as spasms) that could be related to either device or to the medical condition treated by either device. Subjects with implantable pump systems will be evaluated for MR compatibility (susceptibility to magnetic fields) prior to MR imaging.

## 11 STUDY OBJECTIVES AND PURPOSE

### 11.1 Purpose/Objective

We propose an investigation of the safety of deep brain stimulation (DBS) for the alleviation of chronic neuropathic pain in patients with spinal cord injury (SCI). The stimulation will be applied bilaterally or unilaterally in the midbrain periaqueductal-periventricular gray region (PAG/PVG). Indications of efficacy will also be examined. Patients will receive bilateral implants in the case of complete SCI (ASIA-A). Patients with an incomplete SCI who can localize pain to one side of the body will receive unilateral stimulation of the PAG contralateral to the sites of pain.

Although PAG/PVG stimulation has been used previously in SCI pain patients, the small numbers of patients studied and the lack of detail on their testing and injury status makes a phase I trial appropriate. Effective treatment of pain could also bring benefits to patients with autonomic dysreflexia (AD), which can be provoked by painful visceral and somatic stimuli below an incomplete lesion. Autonomic functioning will therefore be studied as a secondary outcome. Preclinical evidence from rats suggests that prolonged PAG stimulation may lead to enduring improvements in all deficits (sensory, motor, and autonomic). The proposed study will therefore examine if such improvements occur when PAG/PVG stimulation is applied over many weeks.

Aim 1 is to determine whether DBS in the PAG/PVG at analgesic intensities produces any systemic or neurological adverse effects in patients with longstanding SCI (>1 year), either immediately or as a result of prolonged application for up to 40 weeks.

Aim 2 is to determine whether acute application of DBS in the PAG/PVG influences the severity of spontaneous ongoing pain caused by longstanding SCI.

Aim 3 is to determine whether DBS in the PAG/PVG affects stimulus-evoked or persistent hypertension (a major sign of autonomic dysreflexia) in chronic SCI patients.

Aim 4 is to determine whether prolonged PAG/PVG stimulation (for 10 months) leads to cumulative changes in chronic pain severity, motor or autonomic symptoms in chronic SCI patients.

### 11.2 Core (null) Hypothesis:

The null hypothesis is that, in humans, deep brain stimulation (DBS) applied bilaterally or unilaterally in the midbrain periaqueductal-periventricular gray region (PAG/PVG) will not alleviate chronic neuropathic pain in patients with spinal cord injury (SCI).

### 11.3 Primary Objectives:

To evaluate the safety and efficacy of deep brain stimulation (DBS) applied bilaterally or unilaterally in the midbrain periaqueductal-periventricular gray region (PAG/PVG) for alleviation of chronic neuropathic pain in patients with spinal cord injury (SCI).

### 11.4 Secondary Objectives:

To assess the clinical effects of DBS on autonomic functioning when PAG/PVG stimulation is applied over many weeks (44 weeks); to determine with Aactiva PC+S whether local field potentials in the PAG/PVG can be used to predict the efficacy of DBS in this region.

## 12 STUDY DESIGN

### 12.1 Type of Study

Phase 1, open label study.

### 12.2 Expected Number of Participants

Twelve (12) participants with SCI for >1 year and show chronic persistent pain that has not fully responded to drug treatment.

### 12.3 Treatment Groups

One (1) Treatment group. All participants will receive the same treatment (long-term DBS in PAG/PVG) and undergo the same procedural protocol. Ethical considerations forbid a control group that receives implant surgery without stimulation. Hence participants must serve as their own controls.

After internalization of the pulse generator (electronic stimulator) and subcutaneous tunneling of connecting cables to the electrode and 12-48 hours for recovery from this internalization procedure, stimulation will be applied to the patient. The patient will be asked to report their ongoing pain level, on a 0-10 numerical rating scale (NRS) with the stimulation turned off and, for each electrode contact, in small voltage steps up to the threshold for any aversive effects (if not seen in the first step). Floating, dizzy or warm feelings can be expected, based on literature reports. If there is no ongoing pain, cutaneous brushing to cause allodynia below the injury, at sensitive sites determined in the pre-surgical testing sessions, will be used. Blood pressure will also be measured by cuff before and during electrical stimulation. This will be repeated on week 12. The optimal level will be 67% of threshold for aversive or other unwanted effects (e.g. motor) or device maximum (10 V) if such effects are not observed. We expect the optimal voltage to be 4-10V. A frequency range of 10-20 Hz and pulse width range of 250-450  $\mu$ s is anticipated, but these parameters will be set according to the subject's responses. The subject returns home with the optimal stimulation settings after each programming session.

Subjects will receive monthly adjustment of stimulation levels to optimize analgesia on the NRS. They will be given the option of remaining in the study if any level becomes unpleasant in later months.

The subject will be given up to 4 different program groups after study week 16, differing in contacts, voltages, frequencies and pulse widths, all determined to be without adverse effect by the clinician programmer in the in-person office session. The subject is asked to switch program groups using their patient programmer. They switch immediately if relief is unsatisfactory, and stay with the best program for pain relief, or with any adequate program if the best is not determined, keeping a pain diary (score 0-10) at intervals of 24 hours or less to help determine the best program group.

If the subject reports effects of DBS on sleep, the stimulation will be cycled in appropriate 12-hour on and off periods in a 4 week trial period and maintained if superior. Also, if the subject does not tolerate continuous stimulation for many hours, cycling at shorter intervals (e.g., one-hour on and off periods) will be tested.

Although all subjects receive the same DBS treatment, a subset will receive the PC+S device for additional sensing of brain signals. After regulatory permissions have been obtained, the next subject to reach surgical consent (stage 3 consent) will receive this device. Subsequent enrollees will also receive the Activa PC+S DBS system.

### 12.4 Schematic diagram ("Study Flow Charts") of trial design, and procedures

- A. Table 1 lists the major procedures relevant to this study.
- B. Table 2 contains the flow sheet which shows the frequency and timing of all visits.

## 12.5 Description of the Measures Taken to Minimize/Avoid Bias

As this is an open label safety study without a control group, no specific measures will be taken (e.g., randomization, blinding, etc.) to minimize /avoid bias. Subjects will not be randomized, and all will receive the same pattern. The subject and the primary evaluator will not be blinded to the stimulation level. Long-term changes over the course of the treatment will be analyzed by time-series analysis of the adjusted stimulation levels. Placebo effects from surgery, as well as the safety and stability of the DBS implant, will be analyzed when the stimulator is inactivated during programming adjustment sessions by investigators.

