#### Aims:

1. To evaluate any changes in pain relief in the 2nd and 3rd year of deep brain stimulation (DBS) in the midbrain periaqueductal/periventricular gray (PAG/PVG).
2. To assess needs for changes in stimulation parameters (contact selection, voltage, frequency, pulse width) to continue optimal relief.
3. To determine changes in injury status revealed by the ASIA score.
4. To uncover later-occurring adverse effects.

Enrollment. Subjects will preferably continue without a gap at the end of the original 52 week study. However, they may be enrolled at any time during the extension to accommodate the time needed to obtain regulatory approval for the extension or subjects who wish to take a break. An additional informed consent form will be used for enrollment.

Procedures. Subjects will receive continuous DBS in the PAG/PVG from the previously implanted system. They will return every 12 weeks to the study site to optimize the stimulation parameters for pain control. The optimum may drift or may not have been determined previously from the very large range of possible settings. Subjects will leave the visits with a blinded choice of settings (2 to 4, labeled A, B, C D), which they can explore at home. Preliminary findings suggest that pain changes over several days when settings are changed, and that slow recursive testing is the best way to find the optimum. Subjects may request visits

at other times for stimulation adjustment or other study related issues. Some later subjects may have a PC+S generator device implanted, which allows recording from the stimulating leads. Subjects with this device will also undergo brief recording sessions during visits, following the protocol of the first year.

Tests and questionnaires. The study extension will use only questionnaires and study forms from the original study. It will omit autonomic system testing and quantitative sensory testing. On-site assessment will be done in clinical exam rooms and offices of the Miami Project to Cure Paralysis of the University of Miami Miller School of Medicine, including ASIA assessment. If the stimulator settings are producing consistent adequate pain relief, visits may be omitted at the subject's discretion, except for weeks 104 and 156, and assessments will be made by telephone questionnaire.

The following will be assessed every 12 weeks.

- International Spinal Cord Injury pain basic data set (ISCI)
- Neuropathic Pain Symptom Inventory (NPSI)

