Urine Pregnancy (note 4)	2		x					x								
HIV, Hep B, Hep C serology	1		x													

1 All General Assessments and Neurological System Exams, i.e., BDI, MMSE, QST, Pain (ISCI PBDS, NPSI, MPI-SCI), PGIC, during this period will occur prior to DBS adjustments.

2 Pain testing may take place at either site

3 Not required if determined subject can't tolerate it to completion

4 Urine pregnancy test for premenopausal women

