### E. Futility and Enrichment:

Gradual benefits may be seen from prolonged treatment. Therefore the study will not be stopped early in the absence of interim benefits, nor will the stimulation intensity be increased.

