### **15 SAFETY**

Participants will be continuously monitored throughout a one (1) year evaluation period. Assessments will be performed as outlined in Table 1 and Table 2 in section 13.6. Assessments will also include monitoring of occurrence of AEs (acute, delayed, and/or cumulative), as well for changes in clinical status, neurological status and/or functional status. Safety will be determined as follows:

- a) Adverse events or other safety concerns will be ascribed to one of two categories: (1) general known problems with all types of DBS (e.g. infection) or with untreated SCI (e.g., bladder control failure); (2) problems caused by the PAG/PVG site in particular (e.g., hypotension) or to a specific response of SCI symptoms to DBS (e.g., more pain). The first category will not lead to ejection of the method. The second category can be evaluated more by turning off the stimulation or examining correlations with the 4-week periods of (8-weeks after week 24) adjustment of stimulation amplitudes. Second-category events will be carefully assessed and will lead to discontinuation of the study treatment if they cannot be ascribed to special circumstances in a given patient.
- b) Comprehensive pain, motor and autonomic assessment will occur on screening and enrollment (baseline) and then on on-site visit weeks (weeks 12, 16, 20, 24, 32, 40, 48 and 52).
- c) The correct functioning of the DBS apparatus will be monitored every 4 weeks, after implantation, until week 24. Thereafter this assessment occurs every 8 weeks, and on the last visit (week 52).
- d) Pain Assessments using the ISCI-PDS:B and neuropathic rating scale will evaluate development of neuropathic pain syndromes.

The secondary hypothesis which concerns autonomic assessment will also take place during routine patient visits. Heart rate, blood pressure, sweating, body temperature and breathing will be classified as normal, abnormal, unknown, or unable to access. Within the abnormal category, sub-categories will be

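### Section 12.5 analyses long-term change through stimulation levels that are themselves set in response to pain, so neither their trend nor their correlation with outcomes can show what DBS does

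*Combined protocol and SAP*

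**What the plan says.** Section 12.5, on bias, gives the method for long-term change: "Long-term changes over the course of the treatment will be analyzed by time-series analysis of the adjusted stimulation levels". It names no model, lag or dependent variable, and it states that neither subject nor primary evaluator is blinded to level.

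Other sections say how the level is set:
- Section 12.3, in clinic: "Subjects will receive monthly adjustment of stimulation levels to optimize analgesia on the NRS".
- Section 12.3, at home after week 16: "They switch immediately if relief is unsatisfactory, and stay with the best program for pain relief".
- Section 12.3, tolerability limit: "The optimal level will be 67% of threshold for aversive or other unwanted effects (e.g. motor) or device maximum (10 V").
- Section 12.6.1, extension: "They will return every 12 weeks to the study site to optimize the stimulation parameters for pain control".
- Section 12.7 E, when interim benefit is absent: "nor will the stimulation intensity be increased".

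Section 15(a) allows events attributed to the stimulation site or to a specific SCI response, with increased pain as an example, to be evaluated by switching stimulation off or by "examining correlations with the 4-week periods of (8-weeks after week 24) adjustment of stimulation amplitudes".

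Note 1 to Table 2 fixes the order at a visit: assessments "during this period will occur prior to DBS adjustments". Section 17.1 makes NRS pain the main dependent variable and expects a lasting change from baseline to 44 weeks after implant. Section 17.2 covers baseline to week 52. Section 17.3 calls all analyses descriptive.

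**The concern.** The analysed quantity is partly a consequence of the outcome. If the level goes up when pain is high and is held or lowered when unwanted effects appear, the level series records how clinicians and patients reacted. A rising series could mean tolerance, worsening disease, or a search for a better setting in someone who is or is not benefiting.

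The same feedback biases any association between level and pain. It also affects adverse events: Appendix 1 (5.6) contemplates lower voltage output in response to moderate or severe events, so an event can appear unrelated to amplitude because amplitude was reduced on its account.

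At stake is the interpretation of Aim 4 (cumulative change over prolonged stimulation) and of events that, under section 15(a), can lead to discontinuation of the study treatment. The model covariates in section 17.1 (injury level, completeness, electrode configuration) do not include prior pain, prior level or time.

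**Working it through.** The documents give no figure for this analysis, so there is none to reproduce. From the documents: 12 participants; 8 on-site visits (weeks 12, 16, 20, 24, 32, 40, 48, 52); NRS read before adjustment; voltage 0.1–10 V. The dose-response, titration gain and SDs below are assumptions.

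**Step 1: why same-visit pairing misleads.** Suppose the new level is V_after = V_before + g × (NRS − 5), with g = 0.5 V per point and everyone starting at 4 V. At the first adjustment V_after = 4 + 0.5 × (NRS − 5), so NRS = 5 + 2 × (V_after − 4). The slope of NRS on the adjusted level is +2 NRS per volt whatever the true effect. It describes the rule.

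**Step 2: does a level trend separate benefit from no benefit?** Model: NRS = 6.5 + patient effect (SD 1.5) + AR(1) error (SD 1.2, autocorrelation 0.7) + β × (V − 4.5). Each visit V changes by gain × (NRS − 3) plus noise (SD 0.3). Start 3–6 V; 1,500 trials per setting. Trends are scaled to 44 weeks.

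| Gain (V per NRS point) | Level trend, β = −0.3 | Level trend, β = 0 | NRS trend, β = −0.3 | NRS trend, β = 0 |
|---|---|---|---|---|
| 0.1 | +2.20 V | +2.46 V | −0.63 | +0.01 |
| 0.2 | +3.36 V | +3.76 V | −1.01 | 0.00 |
| 0.4 | +3.05 V | +3.22 V | −0.92 | −0.01 |

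The level rises either way. The NRS trend separates the two cases when underlying pain is stable.

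**Step 3: sign of the within-person NRS-on-level slope.** Model: NRS = person mean (7, SD 1) + AR(1) drift (0.7, SD 0.8) + β × (V − V_ref) + reading noise (SD 0.8), with V raised 0.5 V per NRS point above 5, start 4 V, 2,000 trials per setting, β from −0.1 to −0.3. The slope is Σ(L − L̄)(NRS − mean NRS) / Σ(L − L̄)², with deviations taken within person. The inputs leave three choices open: whether V is also lowered below NRS 5, whether NRS 7 applies at 0 V or 4 V (V_ref), and whether 0.8 is the innovation or the stationary SD of the drift.

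- NRS paired with the level set after it: wrong sign in about 73–80% of trials with two-way titration, V_ref = 0 and innovation SD 0.8; about 2–66% under the other combinations.
- NRS paired with the level in force before adjustment: wrong sign in at most 8% under all of them. In the first combination the mean slope runs from about −0.14 to −0.38 for a truth of −0.1 to −0.3, a modest overstatement.

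**Step 4: the second pairing is not safe in general.** In the Step 2 model (gains 0.1–0.4), the within-person slope on the level in force had the wrong sign in 16–23% of trials at β = −0.1, 4–8% at −0.2 and 1–4% at −0.3. With β = −0.3, gain 0.2 and pain drifting up 0.4 NRS per visit, it was +0.23 on average and wrong in 99%. Pooling across patients at β = −0.3 gave +0.20 to +0.21, wrong in 80–89%. With the level set independently of pain (gain 0), the pooled slope was −0.32, close to the truth.

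**The case against.** The strongest reply is that section 12.5 never specifies a regression of NRS on level; it may mean only that levels are described over time. A reader might infer that reversed signs are the expected result and that Aim 4 will be answered in the wrong direction. The documents do not support that. Sections 17.1 and 17.2 already make NRS the main dependent variable and look at change from baseline, which does not depend on the level series. Aim 4 also covers motor and autonomic symptoms, which section 12.3 does not make the titration target. Frequent within-person reversal needs the NRS to be paired with the level set after it, together with particular assumptions. Pain is not the only determinant of level either: section 12.3 uses an unwanted-effect threshold and also varies contacts, frequency and pulse width, and section 12.7 E speaks against increases.

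On safety, section 15(a) offers switching stimulation off as well as correlation, and an event that eases after a reduction is informative if timing is examined. No calculation here addresses adverse events.

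All of this limits the size of the problem. It does not rescue the sentence in section 12.5: a purely descriptive level trend still cannot measure long-term change in the patient. Nor does the brief off-check settle the question for pain. Table 2 allows a possible 5-minute inactivation, whereas section 12.6.1 reports that pain shifts over several days after a settings change.

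**Conclusion.** The section 12.5 analysis is wrong as written: it takes as its measure of long-term change a quantity adjusted in response to that change. The level trend is uninformative about benefit under every titrated setting in Step 2. Level–NRS and level–event correlations are biased by titration and can reverse sign. The frequency of reversal is not a property of this trial that can be stated: about 2% to 80% with the level set afterwards, 8% or less with the level in force in the Step 3 simulations, and higher in the Step 4 model when the effect is weak or pain is worsening. All of these rest on assumed effects, gains and SDs.

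The consequence is a risk of misinterpretation in a 12-person, single-arm, descriptive study, not a false test decision. Separately, section 12.3 (levels adjusted for analgesia) and section 12.7 E (no increase when interim benefit is absent) do not agree and must be reconciled, because they imply different level series.

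**What to change.** In section 12.5, replace the analysed variable. The long-term outcome should be the NRS read before each adjustment (Table 2, note 1), modelled on study week with a participant random effect and with each contrast taken against baseline. This agrees with sections 17.1 and 17.2. Report stimulation levels over time descriptively.

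In section 15(a), state that a same-visit correlation of amplitude with an adverse event or with pain is not by itself evidence for or against a relation. Examine the timing of events relative to level changes, and the stimulation-off check, alongside it.

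Reconcile sections 12.3 and 12.7 E.

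The cost is wording only; the data are already scheduled. The change does not remove placebo effects, medication changes (tapering begins at week 20) or natural drift. In the Step 2 model with β = −0.3 and gain 0.2, upward drift of 0.2 NRS per visit turned the NRS trend to +0.23 despite a true benefit, so the single-arm limitation should be stated with the result.
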